6.4 Sample Size and Power

We will enroll up to a total of 25 subjects to generate 20 subjects will have adequate evaluable data, during a proposed 24 month study period. The **Table** shows the number of patients required, with 80% power and $\alpha=0.05$, to detect a range of within subject differences in mean oxygen saturation index (at various within subject standard deviation [SD] levels) between the two treatment periods. As shown, the proposed sample size of 20 subjects will provide sufficient power to detect a range of clinically meaningful differences in oxygen saturation indices with statistical significance.

Table. Minimal detectable difference in mean oxygen saturation index

SD	Detectable difference			
	1	1.5	2	3
0.25	4	3	3	3
0.5	7	5	4	3
1	18	10	7	5
1.5	38	18	11	7
2	65	30	18	10
3	144	65	38	18

6.5 Interim Analysis

Interim analysis for safety will be performed after every 5 subjects are completed to determine the safety and validity of the ventilator management guidelines by the safety monitoring committees at each site.

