Safety Evaluations	Subject safety will be monitored by through assessment of adverse events, vital signs, physical examinations, and laboratory data by the medical and study teams as well as the independent data safety monitoring committee. All study investigators and a core group of respiratory therapists who will care for study infants will be provided training on the Servo I ventilator and the NAVA mode. Clinicians responsible for the care of study subjects receiving the NAVA mode of ventilation will be trained up to the current standard for their role, as is done for clinicians using clinically deployed ventilators. Guidelines for startup and continued management, including troubleshooting techniques of the NAVA mode, will be available for the medical teams and a study investigator will be on call 24/7. Individual subjects will be withdrawn from the study for safety if there is an absolute, sustained increase in FiO ₂ by 20% or if the pCO ₂ /TcO ₂ increase by 25 points above baseline or to a level greater than 90 mm Hg, for more than 2 hours while on the NAVA mode. If this occurs, the patient will discontinue NAVA therapy and be transitioned to previous CMV settings. A study investigator will round daily with the clinical team and be available 24/7 for questions. The overall safety of the study will be assessed with interim safety analyses after the completion of every 5 patients (3 times total) and in the event of any serious safety events.
Statistical and Analytic Plan	Summarized values for the primary and secondary outcomes will be compared between the two treatment arms using paired statistical tests (e.g. Wilcoxon signed rank tests, paired t-tests) as appropriate, based on the data distribution. Linear mixed effects models will be used to explore longitudinal change in the study outcomes (as continuous measures) as a function of the treatment arm.
DATA AND SAFETY MONITORING PLAN	Clinical adverse events will be monitored throughout the study period. There will be monthly and as needed ad-hoc study investigator meetings to discuss and monitor trial data and safety. All data will be kept confidential in accordance with HIPPA and CHOP policies. An independent safety monitoring committee inclusive of physicians from each study site will be formed to review any adverse events, adjudicate relatedness to the study procedures, and recommend trial continuation or early closure.

TABLE 1: SCHEDULE OF STUDY PROCEDURES

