3.3.2 Total Number of Study Sites/Total Number of Subjects Projected

The study will be conducted in two intensive care units at CHOP (NI/ICU and PICU) and the PICU at Hasbro Children's Hospital.

Recruitment will stop when 20 subjects successfully complete the trial. It is expected that approximately 25 subjects will be enrolled to produce 20 evaluable subjects.

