4.3 Subject Completion/Withdrawal

Subjects may withdraw from the study at any time without prejudice to their care. They may also be discontinued from the study at the discretion of the Investigator or attending physician to protect the subject for reasons of safety or for administrative reasons. If the withdrawal occurs during the NAVA mode phase of the trial, each site will return the subject to a ventilator platform that is routinely used at their site, selected at the discretion of the treating physician. It will be documented whether or not each subject completes the clinical study. If the Investigator becomes aware of any serious, related adverse events after the subject completes or withdraws from the study, they will be recorded in the source documents and on the CRF. Specific subject and study stopping rules are outlined in section 5.

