5.2 Safety Evaluation

Subject safety will be monitored by adverse events, vital signs, physical examinations, and laboratory data by the medical and study team as well as the independent safety monitoring committee.

Clinicians responsible for the care of study subjects receiving the NAVA mode of ventilation will be trained up to the current standard for their role, as is done for clinicians using clinically deployed ventilators (as listed in section 8.4.2). Guidelines for startup and continued management, including troubleshooting techniques, of NAVA mode will be available for the medical teams and a study investigator will round with the clinical team daily to provide expertise on the device/mode as well as be on call for assistance 24/7. Individual subjects will be withdrawn from the study for safety if an absolute increase in FiO_2 by 20% or if the $\text{pCO}_2/\text{TcO}_2$ increase by 25 points or greater than 90 mm Hg, which ever is achieved first, for more than 2 hours from baseline while on NAVA mode, The NAVA arm of the study will be discontinued and the patient will be transitioned to previous CMV settings. Study investigators will be available 24 hours day when a patient is on the trial.

The overall safety of the study will be assessed with interim safety analysis after the completion of every 5 patients (3 times total) and upon any serious safety events occurring.

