8.4 Regulatory and Ethical Considerations

8.4.1 Data and Safety Monitoring Plan

Clinical adverse events will be monitored throughout the study period. There will be monthly and as needed ad-hoc meetings among the study investigators to discuss and monitor data and safety. All data will be kept confidential in accordance with HIPPA and CHOP policies. An independent safety monitoring committee (DSMC) will be formed to review any adverse events that occur and determine if they are related to the study or the natural course of this critical illness. The DSMC will have a representative make up of 3 physicians represented by each specialty involved with these patients (neonatologist, pediatric intensivist, and pediatric pulmonologist). The DSMC will meet as needed to discuss patient specific concerns as well review data at the planned interim analysis after every 5 patients.

CHOP PI will monitor and review the study progress, subject safety, and the accuracy and security of the emerging data at CHOP, and will report any adverse events in accordance with the FDA regulations and IRB policies.

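### The scheduled interim safety reviews count only completed infants, so they come later as withdrawals on NAVA rise

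*Combined protocol and SAP*

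**What the plan says.** - **Scheduled trigger.** Section 6.5: "Interim analysis for safety will be performed after every 5 subjects are completed". The synopsis (safety evaluations) has "interim safety analyses after the completion of every 5 patients (3 times total) and in the event of any serious safety events", and section 5.2 repeats both the schedule and the event-driven addition. Section 8.4.1 gives the interval as 5 patients and does not say that they must have completed.
- **Completion.** The term is not defined. Section 4.3, which deals with withdrawal, says "It will be documented whether or not each subject completes the clinical study". Section 3.3.2 says "Recruitment will stop when 20 subjects successfully complete the trial".
- **Exit rule.** The synopsis and section 5.2 withdraw an infant from the study when FiO2 or CO2 passes a stated limit for more than 2 hours on NAVA. No matching rule is stated for CMV.
- **Who reviews.** Section 6.5 assigns the review to be done "by the safety monitoring committees at each site". Section 8.4.1 says "An independent safety monitoring committee (DSMC) will be formed to review any adverse events", made up of three physicians by specialty, who also meet as needed. The synopsis describes one independent committee with physicians from each site, which may recommend early closure.
- **Study-level rule.** Section 4.3: "Specific subject and study stopping rules are outlined in section 5". Section 5 holds individual withdrawal criteria and the review schedule, but no study-level rule.

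**The concern.** The scheduled review exists to judge whether the ventilator guidelines are safe and workable. An infant who has to leave NAVA is the most direct evidence on that question, yet on the ordinary reading that infant does not count towards the next look. The timing of the look then depends on the harm it is meant to detect, and in the wrong direction.

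The event-driven review does not clearly close the gap. No section defines a serious safety event or says that a withdrawal on the FiO2 or CO2 criteria is one. Section 7.2 sends notable non-serious events to the IRB at continuing review. Several infants could therefore leave NAVA on gas-exchange grounds before any text obliges the committee to look at the accumulating number. Section 8.4.2 names respiratory decompensation as a risk at the site where the mode is less familiar. The conflicting committee descriptions and the unmatched reference to study stopping rules also leave unclear who would look, and against what.

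**Working it through.** **1. The plan's own figure.** Looks fall at multiples of 5 below the final count. With 20 completers (section 3.3.2) these are 5, 10 and 15, which gives the stated three. With 25 enrolled (section 6.4) they would be 5, 10, 15 and 20, which is four. The stated three therefore fits a count of completers. The enrolment figure also reproduces: 20/(1 − 0.20) = 25.

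**2. Inputs.** Let w be the share of infants who leave before completing. The documents give no rate by mode. The only anchor is 25 enrolled for 20 evaluable, an implied 20% for all causes; every other value of w below is an assumption. Infants are taken to be withdrawn independently of one another.

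**3. Formulas.**
- Expected number enrolled at the first look: 5/(1 − w).
- Expected withdrawals by then: 5w/(1 − w).
- Chance of 3 or more withdrawals before the fifth completer (negative binomial): 1 − (1 − w)^5 × (1 + 5w + 15w²).
- Chance of reaching the third look within 25 enrolled: P(Binomial(25, 1 − w) ≥ 15).

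At w = 20%: 5/0.8 = 6.25, and 1 − 0.32768 × 2.6 = 0.148. At w = 40%: 5/0.6 = 8.33, and 1 − 0.07776 × 5.4 = 0.580.

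| w | Enrolled at first look | Withdrawn by then | Chance of 3 or more withdrawn before it | Chance the third look is reached |
|---|---|---|---|---|
| 0% | 5 | 0 | 0% | 100% |
| 10% | 5.6 | 0.6 | 3% | over 99% |
| 20% | 6.3 | 1.3 | 15% | 99% |
| 30% | 7.1 | 2.1 | 35% | 90% |
| 40% | 8.3 | 3.3 | 58% | 59% |
| 50% | 10.0 | 5.0 | 77% | 21% |

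**4. In time.** If 25 infants accrue evenly over 24 months, the number enrolled at the first look is reached at 5/(1 − w) × 24/25 months: 4.8 at w = 0, 6.0 at 20% and 8.0 at 40%. This leaves out the treatment days themselves.

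**5. With withdrawals counted.** The first look falls at 5 infants whatever w is. Expected withdrawals at that look are 5w: 1.0 at 20% and 2.0 at 40%, against 1.3 and 3.3 now. If all 25 enrol, the looks are at 5, 10, 15 and 20.

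None of these figures applies to event-driven or as-needed reviews.

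**The case against.** The strongest reply is that the scheduled look is one safeguard among several. The synopsis and section 5.2 require a review on any serious safety event. Section 8.4.1 has the committee review adverse events as they occur and meet when needed, and the investigators meet monthly. An investigator rounds daily, and section 8.5 allows only two infants in the trial at once. All of this stands. A reader might infer that safety review as a whole comes later when NAVA does worse, or that the scheduled look is the only study-level protection. The documents support neither: the delay affects the scheduled looks only.

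A reader might also take section 6.5 to mean that each site counts its own five, so that a site with fewer than five completers is never reviewed and nobody sees pooled data. That rests on one phrase about who reviews. The synopsis and section 8.4.1 describe a single committee, and three looks in total fits pooled counting at 5, 10 and 15. What remains is a contradiction about the reviewing body. It is separate from the delay and does not cause it.

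Two further points are fair. Completion is undefined and section 8.4.1 omits the word, so the completer reading is the ordinary one but not beyond dispute. And at the plan's own 20% the shift is small, just over one infant.

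**Conclusion.** The point holds for the scheduled looks. On the ordinary reading of sections 3.3.2, 4.3, 5.2 and 6.5, an infant withdrawn on NAVA does not advance them, so they slip as withdrawals rise. The direction does not depend on the rate, but the size does. At the 20% allowance the effect is modest and the third look is almost certain to occur. At 40%, which is purely an assumption, more than half of such trials would have three or more withdrawals before the first look, and about four in ten would never reach the third. The other reviews are not delayed, but no text ties a gas-exchange withdrawal to them. The inconsistent trigger wording, the conflicting committee descriptions and the missing study-level rule are contradictions to reconcile, not evidence that oversight is absent.

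**What to change.** - In the synopsis and sections 5.2, 6.5 and 8.4.1, trigger the scheduled review after every 5 infants whose study participation has ended by completion or withdrawal, counted over both sites. Tie completion to the end of the 11-day treatment phase, because the synopsis says that participation lasts until discharge.
- Update the stated three looks: there could be up to four if 25 infants enrol.
- Reconcile the committee descriptions in the synopsis and sections 6.5 and 8.4.1, so that one committee reviews pooled data.
- State whether a withdrawal on the section 5.2 criteria counts as a serious safety event for the event-driven review.
- Reconcile section 4.3's reference to study stopping rules with section 5, which gives only individual criteria.

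Counting from randomisation or from the start of NAVA would also stop the delay, but it would bring in infants with no NAVA exposure or only hours of it. Counting ended participation avoids this. The cost is protocol wording, possibly one extra look, and fewer complete 11-day records at each look. No added data collection is needed.

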7 SAFETY MANAGEMENT

7.1 Clinical Adverse Events

Clinical adverse events (AEs) will be monitored throughout the study.

7.2 Adverse Event Reporting

Study procedures that are greater than minimal risk are the use of the servo I ventilator and the NAVA mode at CHOP. While the servo ventilator is approved for clinical care at CHOP, the NAVA mode is not widely used and may be unfamiliar to some of the medical staff. Section 5.2 and 8.4.2 more explicitly discuss the risks and mitigation of these risks. Targeted adverse event monitoring will occur from study start to 72 hours after the intervention phase has concluded.

Although no SAEs are expected, if any unanticipated problems related to the research involving risks to subjects or others happen during the course of this study (including SAEs) they will be reported to the IRB in accordance with CHOP IRB SOP 408: Unanticipated Problems Involving Risks to Subjects. AEs that are not serious but that are notable and could involve risks to subjects will be summarized in narrative or other format and submitted to the IRB at the time of continuing review.

8 STUDY ADMINISTRATION

8.1 Treatment Assignment Methods

8.1.1 Randomization

Computer generated randomization will determine the initial mode of mechanical ventilation. There will be 1 randomization scheme for the entire study (to be used by both sites) to ensure equal allocation of each ventilation mode as the starting mode. Investigators and clinicians will not be blinded to the mode of ventilation as this information is essential for patient management and is easily discovered. However, blinded data analysis will be performed.

8.2 Data Collection and Management

The information collected will be entered into the password protected computerized database REDCap and house on the CHOP server. Confidentiality will be ensured from abstraction through analysis by utilizing the HIPPA functions in REDCap. To ensure security, a copy of the data collected will be saved in a Research share drive on the CHOP server with only study team members having access. Data will be downloaded from the ventilators and monitoring devices and saved to the research share drive by study ID number. All Identified data will be maintained and destroyed in compliance with CHOP Policy A-3-9.

Saliva specimens transferred for analysis of cortisol levels will be done under material transfer and data use agreements. Saliva specimens will only be marked with study ID number and day of sample. No identifiable information will be transferred with the specimens.

8.3 Confidentiality

All data and records generated during this study will be kept confidential in accordance with Institutional policies and HIPAA on subject privacy and that the investigator and other site personnel will not use such data and records for any purpose other than conducting the study.

No identifiable data will be used for future study without first obtaining IRB approval. The investigator will obtain a data use agreement between the provider (the PI) of the data and any recipient researchers (including others at CHOP) before sharing a limited dataset.

8.4 Regulatory and Ethical Considerations

8.4.1 Data and Safety Monitoring Plan

Clinical adverse events will be monitored throughout the study period. There will be monthly and as needed ad-hoc meetings among the study investigators to discuss and monitor data and safety. All data will be kept confidential in accordance with HIPPA and CHOP policies. An independent safety monitoring committee (DSMC) will be formed to review any adverse events that occur and determine if they are related to the study or the natural course of this critical illness. The DSMC will have a representative make up of 3 physicians represented by each specialty involved with these patients (neonatologist, pediatric intensivist, and pediatric pulmonologist). The DSMC will meet as needed to discuss patient specific concerns as well review data at the planned interim analysis after every 5 patients.

CHOP PI will monitor and review the study progress, subject safety, and the accuracy and security of the emerging data at CHOP, and will report any adverse events in accordance with the FDA regulations and IRB policies.

8.4.2 Risk Assessment

The risks in this study associated with passing a second tube into the esophagus (the NAVA catheter) for research purposes is minimal, with a low probability of associated harm. The risk of inserting this tube for research purposes is no greater than inserting a feeding tube or temperature catheter. The insertion of these devices for clinical purposes is performed by nursing staff and is done frequently in the NI/ICU and PICU for almost every patient. The risk of esophageal perforation from the catheter used for Edi measurements is the same as that for routine insertion of feeding tubes done at the bedside and is extremely rare. The treatment for this complication consists of withdrawal of the tube and a course of antibiotics as the perforation heals naturally.

The proper positioning of the NAVA catheter will be confirmed with a positioning identification software on the Servo I ventilator. There will be continuous monitoring of vital signs throughout the study in accordance with unit standards. A respiratory therapist specially trained in NAVA mode will care for the study patient 24 hours a day and a study physician will be available for consultation throughout the study to ensure safety and comfort of the patient and consultation for any ventilator adjustments. NAVA is an FDA approved mode of ventilation for subjects currently available and used commonly in children with other disease processes routinely at other hospitals. This mode is commonly used at other hospitals for sBPD and other diseases; however, the efficacy of its use compared to conventional ventilation has not been adequately studied.

To measure the transcutaneous CO₂, a probe is placed on the skin in a fleshy area of the body and it heats the skin. Often times a temporary red mark is left when the probe is removed and there is a small chance of burning of the skin if the probe is left in place for too long. For this reason, nursing and respiratory therapy staff routinely rotate the position of the probe.

For CHOP site only (as Hasboro site already used Servo U ventilators and the NAVA mode): There is a risk to the introduction of a less familiar mode of ventilation that is not widely used at CHOP. Lack of knowledge and expertise by the clinical team on the use of this mode can lead to decompensation in the respiratory status of the patient (i.e. reduction in SpO₂, increase in CO₂, increased heart rate, increase in work of breathing, and cardio respiratory arrest, and death). The risk of use of this mode is the same as the use of any of the modes of ventilation that are not widely used but on the multitude of ventilation devices available at CHOP. Each ventilator has approximately 12 modes of ventilation that can be used with only about 4 or 5 that are widely used. As an example, The Drager V500 ventilator, the primary ventilator platform at CHOP, has 14 modes and only 6 of them are commonly used in all ICU's. To assist in minimizing this risk to subjects, all clinical staff members that will care for these subjects will be trained on the use of the Servo I ventilator in accordance with the standards of ventilator training for their role. The current standard for each roll is:

- Nursing – in-servicing and hands on training limited to modes, reading of settings and monitoring parameters, adjustment of FiO₂, and alarm silence
- Physicians/FLC's – in-servicing on modes, reading of setting and monitoring parameters, and ordering
- Respiratory Therapists – in-servicing on modes, ventilator functionality, patient set-up, setting of parameters and alarms, reading of monitoring parameters, troubleshooting, and cleaning completed with competency check off

Only trained and certified respiratory therapists will be assigned to care for patient on study 24/7. Guidelines for escalation and de-escalation of care will be available at the bedside of all subjects. A study investigator will provide a physical assessment of the subject and round daily with the clinical team to provide expertise on the mode of ventilation as well as be available 24/7 for questions. Additionally, when the subject is in the NAVA mode arm of the study, the Drager ventilator will remain in the patient room and be ready for immediate use if needed. The medical team will always have the option for safety or preference reasons to transition the subjects back to the standard Draeger ventilator used for routine clinical care. An additional safety feature of the NAVA mode is the mandated input of back-up ventilation settings as described in section 1.2 of the protocol.

Collection of salivary cortisol presents no more than minimal risk as it is less invasive than the mouth care these children receive on a daily basis

